Prognosis in HMA-failure patients is extremely poor. Jabbour et al⁹ report a median survival of merely 4 months in MDS patients with progressive disease after decitabine (Figure 1), and Prebet et al⁷ identified a similar median survival of 5.6 months in MDS patients with progressive disease after 5-azacytidine. There are no currently approved agents in the setting of HMA-failure MDS patients, and there are limited therapeutic options, particularly given the increased age and frequent comorbidities of this population.

As alluded to above, the platelet count in MDS patients is critically important, and impacts both treatment decisions and overall survival in the majority of MDS patients. Among 2410 patients with MDS referred to the MD Anderson Cancer Center, 67% had a platelet count $<100 \times 10^9/L$ at the time of their initial consultation, and even within the lower-risk MDS categories, over 10% of patients experience life-threatening thrombocytopenia ($<20 \times 10^9/L$) at presentation.¹⁰ Thrombocytopenia has been identified as an independent and adverse prognostic factor for overall survival in MDS at all stages.¹¹ An analysis of 892 primary MDS subjects identified a median survival in patients with platelet counts $< 100 \times 10^9/L$ of 27 months, compared to 60 months for patients with platelet counts $\geq 100 \times 10^9/L$.¹² Furthermore, the mainstay of treatment for thrombocytopenia in MDS patients, transfusions, are short-lived, and associated with transfusion reactions, allo-immunization, transmission of bacterial and viral infections, and have no impact on the underlying disease biology.

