4. TREATMENT PLAN

4.1 Study Design

This is a two arm phase II study to evaluate the safety and efficacy of high dose eltrombopag for the treatment of MDS patients with thrombocytopenia after experiencing hypomethylating agent (HMA) failure. The primary efficacy endpoint is the overall response rate (ORR) based on the IWG-2006 criteria, which includes complete remission (CR), partial remission (PR), and major hematologic improvement (HI). Patients' overall response will be assessed after at least 2 cycles of treatment and no more than after 6 cycles of treatment and each cycle is 28 days. A total of 46 patients will be enrolled into two arms: (A) eltrombopag only or (B) eltrombopag with continuation of the hypomethylating agent. All patients will be accrued from M. D. Anderson Cancer Center (MDACC).

4.1.1 Arm A: Eltrombopag monotherapy in 28-day cycles.

4.1.2. Arm B: Eltrombopag in combination with continuation of hypomethylating agent in 28-day cycles. The choice of HMA agent (e.g. azacitidine or decitabine) will be the HMA the patient has received prior to enrollment on study. Eltrombopag should be initiated at the start of the next HMA cycle whenever possible so the start date of both agents is consistent. Subsequent cycles will begin on the first day of Decitabine or Azacitidine therapy, and in the absence of toxicity, Eltrombopag administration will not be interrupted. HMA dosing and dosing adjustments should be performed according to the approved package insert, or alternatively at a dose of decitabine 20mg/m² IV over 1 hour for 5 days every 4 weeks and/or according to the institution's standard of care (see Section 4.7.2 for rules of dose reduction or delay).

4.1.2.1. For patients on Arm B, discontinuation of the hypomethylating agent and continued therapy with eltrombopag monotherapy after cycle 2 of combination therapy may be considered at the discretion of the investigator.

4.1.3. Study Replacement: Study patients that discontinue during cycle 1 of the study for reasons other than toxicity or progressive disease will be replaced.

4.1.4. Treatment Extension: After 12 cycles, subjects experiencing continued clinical benefit and no clinically significant study-drug related grade ≥ 3 toxicity may be eligible to continue therapy after discussion with the PI, and the discussion documented in the patient's medical record.

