6. RESPONSE DEFINITIONS

6.1. Patients' overall response will be assessed after at least 2 cycles of treatment but no more than after 6 cycles, and each cycle is 28 days.

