6.2. Study Endpoints

6.2.1. Primary Efficacy Endpoint: The overall response rate (CR + PR + HI) based on the IWG-2006 criteria. Responses must last at least 4 weeks.

Complete Remission:

- Bone marrow: $\leq 5\%$ myeloblasts with normal maturation of all cell lines
- Persistent dysplasia will be noted
- Peripheral blood
 - o Hemoglobin $\geq 11\text{g/dL}$
 - o Platelets $\geq 100 \times 10^9/\text{L}$
 - o Neutrophils $\geq 1.0 \times 10^9/\text{L}$
 - o Blasts 0%

Partial Remission:

- All CR criteria if abnormal before treatment except:
 - o Bone marrow blasts decreased by $\geq 50\%$ over pretreatment but still $> 5\%$

Stable Disease:

- Failure to achieve at least PR, but no evidence of progression for >8 weeks

Failure:

- Death during treatment or disease progression characterized by worsening of cytopenias or significant increase in percentage of bone marrow blasts

Hematologic Improvement (HI) Response Criteria*: responses must last at least 8 weeks

- **Erythroid response** (if pretreatment hemoglobin $< 11\text{g/dL}$)
 - o Hemoglobin increase by $\geq 1.5\text{g/dL}$
 - o Relevant reduction of units of RBC transfusions by an absolute number of at least 4 RBC transfusions/8 wk compared with the pretreatment transfusion number in the previous 8 wks. Only RBC transfusions given

for a Hgb of ≤ 9.0 g/dL pretreatment will count in the RBC transfusion response evaluation

- **Platelet response** (if pretreatment platelets $< 100 \times 10^9/L$)
 - o Absolute increase of $\geq 30 \times 10^9/L$ for patients starting with $> 20 \times 10^9/L$ platelets
 - o Increase from $< 20 \times 10^9/L$ to $> 20 \times 10^9/L$ and by at least 100%
- **Neutrophil response** (if pretreatment $< 1.0 \times 10^9/L$)
 - o At least 100% increase and an absolute increase of $> 0.5 \times 10^9/L$

*Pretreatment counts averages of at least 2 measurements (not influenced by transfusions) for at least one week

Progression or relapse after HI‡:

- At least 1 of the following:
 - o At least 50% decrement from maximum response levels in granulocytes or platelets
 - o Reduction in hemoglobin by ≥ 1.5 g/dL
 - o Transfusion dependence
- ‡In the absence of another explanation, such as acute infection, repeated courses of chemotherapy (modification), gastrointestinal bleeding, hemolysis, and so forth. It is recommended that the 2 kinds of erythroid and platelet responses be reported overall as well as by the individual response pattern.

Relapse after CR or PR:

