6.3.2. Efficacy Analysis Set

The efficacy analysis set will consist of all enrolled subjects who have received at least one cycle of investigational product. Analysis for efficacy endpoints will utilize this analysis set.

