8.2. Futility Monitoring

8.2.1. For patients treated in Arm A (eltrombopag alone), we assume a target ORR of 18% and a response rate of 5% or lower will be considered not desirable. With a 1-sided type I error rate of 10.3% and 80% power, we will enroll 15 patients in the first stage. If none of these patients achieve OR, the trial will be stopped. If 1 or more out of the first 15 patients have OR, accrual will continue until a total of 23 patients have been enrolled. At the end of the study, if 3 or more out of these 23 patients achieve OR, the treatment of eltrombopag alone will be considered efficacious and is worth further investigation. Under this Simon's Minimax two-stage design, the probability of early termination is 46.3% if the true ORR is 5% and the expected sample size is 19 patients.

For patients treated in Arm B (eltrombopag in combination with HMA), the target ORR is 25%, and a response rate of 5% or lower will be considered not desirable. With a 1-sided type I error rate of 3% and 85% power, we will enroll 12 patients in the first stage. If none of these 12 patients achieve OR, the trial will be stopped. If 1 or more out of the first 12 patients have OR, accrual will continue until a total of 23 patients have been enrolled. At the end of the study, if 4 or more of these 23 patients achieve OR, the treatment of eltrombopag in combination with HMA will be considered efficacious and is worth further investigation. Under this Simon's Minimax two-stage design, the probability of early termination is 54% if the true ORR is 5% and the expected sample size is 17 patients.

Patient enrollment will be suspended if for an arm the first-stage patients have been enrolled and none of these first-stage patients has OR. Accrual will resume if at least one OR is observed within 2 cycles among the first-stage patients for that arm.

8.2.2. The accumulating data will be summarized at regular intervals to provide an ongoing assessment of the safety and efficacy of eltrombopag in this population. Additional summaries of data may be provided for regulatory or publication activities.

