8.4.2. Analysis of Key Study Endpoints

The primary endpoint is overall response rate (ORR). The ORR in each arm will be evaluated along with the exact 95% confidence interval. Given the limited sample size, no formal comparison will be made between these two arms in terms of ORR.

Secondary endpoints include platelet response, durable platelet response, transformation to AML, incidence of bone marrow fibrosis, and time-to-event outcomes such as progression-free survival (PFS) and overall survival (OS). The probabilities of PFS and OS will be estimated using the method of Kaplan and Meier. The incidence rates of other binary secondary endpoints will be estimated, along with the exact 95% confidence intervals. Subjects that discontinue the study prior to having achieved a clinical response will be considered to have not had an event.

Patients receiving growth factors other than eltrombopag (erythropoietin, GM-CSF or G-CSF) will not be considered in the HI analysis for the time periods specified in Section 4.5.3 Supportive Care Guidelines. Hemoglobin levels and platelet counts collected from patients that have received a transfusion within the last 3 days will not be considered in the analysis.

Survival or times to failure and time to progression functions will be estimated using the Kaplan-Meier method. The two-sided log-rank test will be used to assess the differences of time to events between groups.

The total number of dose administrations, the average dose (mg), and the cumulative dose administered will be summarized by eltrombopag treatment group.

Blood chemistry and complete blood counts will be summarized by treatment group at each time point.

Additional exploratory analyses of the key study endpoints will be performed as deemed appropriate.

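### Replacing cycle-1 exits can take certain non-responders out of the 15, 12 and 23 patients behind the go/no-go rules, so the ORR may be biased upward

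*Combined protocol and SAP*

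**What the plan says.** All references are to the combined protocol and SAP.

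- **Replacement, 4.1.3:** "Study patients that discontinue during cycle 1 of the study for reasons other than toxicity or progressive disease will be replaced". The sentence mentions neither death nor the denominator of the response rate.
- **Efficacy set, 6.3.2:** "The efficacy analysis set will consist of all enrolled subjects who have received at least one cycle of investigational product".
- **Failure, 6.2.1:** "Death during treatment or disease progression characterized by worsening of cytopenias or significant increase in percentage of bone marrow blasts". Death during treatment counts whatever its cause.
- **Timing, 6.1:** "overall response will be assessed after at least 2 cycles of treatment but no more than after 6 cycles". Section 6.2.1 adds a minimum duration of 4 weeks for a response and 8 weeks for hematologic improvement.
- **Decision rules, 8.2.1:** In Arm A, "we assume a target ORR of 18% and a response rate of 5% or lower will be considered not desirable". The arm stops on 0 responses in 15 and succeeds "if 3 or more out of these 23 patients achieve OR". Arm B has a 25% target and the same 5% null; it stops on 0 in 12 and succeeds with 4 or more in 23. Both totals are counted as patients enrolled.
- **Discontinuers, 8.4.2:** "Subjects that discontinue the study prior to having achieved a clinical response will be considered to have not had an event". This sentence stands in the paragraph on secondary endpoints.

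**The concern.** The replacement decision is made after treatment has started, and it depends on the recorded reason for leaving. The protocol describes no blinding. Only toxicity and progression are protected from replacement. A treated patient who withdraws for another reason in cycle 1 fits the rule, and so may one whose death is attributed to neither toxicity nor progression.

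Every such patient is a non-responder. If the replacement takes that patient's place among the 15, 12 or 23, a certain zero is exchanged for someone who may respond. Relative to the rate among all treated patients, that can only raise the ORR.

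The decision margins are single patients. One response in the first stage keeps an arm open, and three or four responses make it a success. At stake are the stated error rates and the meaning of the reported ORR.

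**Working it through.** **1. Reproduce the design.** The inputs are the 8.2.1 rules at a true ORR of 5%. The success probability is the sum, over first-stage counts x of at least 1, of P(x) times the chance that stage 2 supplies the rest.

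Arm A (15 patients, then 8):
- P(0) = 0.95^15 = 0.463, which is the stated early-termination probability of 46.3%.
- Type I error = P(1) × P(stage 2 ≥ 2) + P(2) × P(stage 2 ≥ 1) + P(≥ 3) = 0.3658 × 0.0572 + 0.1348 × 0.3366 + 0.0362 = 0.1025.
- Expected size = 15 + 0.537 × 8 = 19.3.

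Arm B (12 patients, then 11):
- P(0) = 0.95^12 = 0.540, against a stated 54%.
- Type I error = 0.3413 × 0.0152 + 0.0988 × 0.1019 + 0.0173 × 0.4312 + 0.0022 = 0.0250.
- Expected size = 12 + 0.460 × 11 = 17.1.

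The same formula at 18% and 25% gives power of 80.2% and 85.4%. The design therefore reproduces. The stated 10.3% and 3% hold as upper limits on 10.25% and 2.50%.

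**2. Add replacement.** Suppose k patients are replaced, so that 23 + k are treated and 23 counted. The replaced share is d = k/(23 + k). If the ORR among all treated patients is 5%, the rate among counted patients is 0.05/(1 − d) = 0.05 × (23 + k)/23. The 8.2.1 rules are then evaluated at that rate. The documents give no replacement rate, so k is an assumption.

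| Replaced per arm | d | Rate among counted | Type I error A | Type I error B |
|---|---|---|---|---|
| 0 | 0% | 5.00% | 10.25% | 2.50% |
| 1 | 4.2% | 5.22% | 11.3% | 2.9% |
| 2 | 8.0% | 5.43% | 12.4% | 3.3% |
| 3 | 11.5% | 5.65% | 13.5% | 3.7% |

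For one replacement in Arm A, the sum is 0.3696 × 0.0618 + 0.1424 × 0.3486 + 0.0403 = 0.113.

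The success boundary also changes meaning. With two replaced, 3/23 = 13.0% is really 3/25 = 12.0% of treated patients, and 4/23 = 17.4% is 4/25 = 16.0%.

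**3. Rough scale for deaths.** Section 2.1 cites one series that "report a median survival of merely 4 months in MDS patients with progressive disease after decitabine" and another with a median of 5.6 months. Under a constant hazard (an assumption), 28-day mortality is 1 − 0.5^((28/30.44)/4) = 14.7%, or 10.8% with 5.6 months. If every such death were replaced, type I error would be 14.6% or 13.2% in Arm A and 4.1% or 3.6% in Arm B. This overstates the effect of deaths. Deaths attributed to progression or toxicity are not replaceable, and the cited medians belong to patients with progressive disease, whereas section 3.1 also admits patients with persistent cytopenias and every IPSS category.

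**The case against.** A reader might infer that 4.1.3 by itself strikes cycle-1 deaths from the count, and that the ORR is therefore certainly biased. The documents do not support that.

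- Section 4.1.3 speaks of discontinuing and does not name death. The lists of reasons for ending treatment in 4.6 and 5.6 do not name it either, and 6.2.1 classes it as Failure. A cycle-1 death can be read as a counted Failure.
- Section 8.2.1 counts patients enrolled, which would keep early exits in. Section 8.4.2 treats those who leave before a response as non-events, although within the secondary-endpoint paragraph.
- The text that actually drops cycle-1 exits from the efficacy analysis is 6.3.2. It also drops exits for toxicity and progression, which 4.1.3 does not replace.
- Toxicity and progression, the reasons most closely tied to outcome, are already protected. Some patients who leave through clinical decline would meet the progression criteria in 6.2.1.
- If the 5% null was meant for patients who complete cycle 1, type I error is not inflated.

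These points stand, and they reduce the finding from certain to possible bias. They do not remove it. A replacement ordinarily takes the earlier patient's place. If replaced patients stayed in the count, the arm would exceed 23 and the boundaries of 3/23 and 4/23 would no longer apply as written. The documents never say which patients make up the 15, 12 and 23.

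**Conclusion.** The concern holds as an unresolved denominator with a possible bias in one direction. Sections 4.1.3 and 6.3.2 and the fixed 23 per arm favour leaving early exits out; 8.2.1 and 8.4.2 favour keeping them in.

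If they are left out, and if the 5% null refers to all treated patients, the inflation is modest: about 1 percentage point per replacement in Arm A and about 0.4 in Arm B. A reader might conclude that both stated error rates fail at once. They do not: with one replacement Arm B is at 2.9%, still inside its 3%. The replacement count is assumed, and the cited survival medians cannot supply it for this mixed population. The change is worth making because it is cheap and the decisions turn on single patients.

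**What to change.** Change four places together. Amending 4.1.3 alone would leave 6.3.2 excluding the same patients.

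- **4.1.3:** only patients who receive no dose of eltrombopag are replaced.
- **6.3.2:** the efficacy set is every patient who receives at least one dose.
- **8.2.1:** the first-stage 15 and 12 and the final 23 are dosed patients. Anyone without a documented response, including a cycle-1 death or withdrawal, is a non-responder.
- **8.4.2:** state that the non-event rule for early discontinuers also applies to the primary ORR.

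An ORR among patients who complete cycle 1 can be reported as a sensitivity analysis.

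For a 5% ORR among all treated patients, this restores type I error of 10.25% and 2.50%. The cost is a slightly lower observed ORR and possibly some power:

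- If the 18% and 25% targets already describe all treated patients, power stays at 80.2% and 85.4%.
- If they describe cycle-1 completers, 5% early exits reduce the effective rates to 0.18 × 0.95 = 17.1% and 0.25 × 0.95 = 23.75%, with power of about 77% and 82%.
- With 10% early exits the rates are 16.2% and 22.5%, with power of 73.5% and 78.4%.

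The plan should say which population the targets describe. No dose or treatment rule changes.

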4.1.5 General

Adverse events, bleeding events, and concomitant medications will be assessed continually throughout the study; specific information will be requested at every study visit.

4.2. Study Duration

4.2.1. All subjects must complete a screening visit, day 1 visits for each new cycle, an end of treatment visit and whenever possible, an end of study safety visit 28 days after the last dose of eltrombopag.

4.2.2. Patients may remain on study for up to 12 cycles if the patient demonstrates clinical benefit and no excessive toxicity (i.e. no clinically significant study-drug related grade ≥ 3 toxicity). Patients who are experiencing clinical benefit and have not experienced excessive toxicity may be eligible to continue therapy after discussion with the PI and the discussion documented in the patient's medical record.

4.3. Administration of eltrombopag, +/- decitabine and azacitidine

4.3.1. Decitabine and azacitidine may be administered by local doctor or at MD Anderson, inclusive of the Regional Cancer Centers (RCC). Commercial supplies of decitabine and azacitidine will be used and records will be obtained from the local physician as indicated in the Dear Doctor letter (Appendix F). Eltrombopag is self-administered.

4.3.2. Eltrombopag should be taken on an empty stomach (1 hour before or 2 hours after a meal). Allow a 2-hour interval before or a 4 hour interval after eltrombopag and other medications (e.g., antacids), calcium-rich foods (e.g., dairy products and calcium fortified juices), or supplements containing polyvalent cations such as iron, calcium, aluminum, magnesium, selenium, and zinc.

4.3.3. Outside physician participation during treatment is acceptable. Documentation of MDACC physician communication with the outside physician will be required. Protocol required evaluations outside MDACC will be documented by telephone, fax or email. All serious adverse events (SAEs) that occur will be reported to the research nurse and will be evaluated by the Principle Investigator within 48 hours of observing or learning of the

event for reportability to the FDA (Appendix F). Fax and/or email will be dated and signed by the MDACC physician. For protocol required labs that are completed outside MDACC, the PI or treating physician must review results for clinical significance and sign and date results. The screening visit, start of treatment visit (Cycle 1 Day 1), and the end of treatment assessment must be performed at MDACC. MDACC visits must occur at least every 3 months on study, and all study bone marrow assessments should be performed at MDACC.

4.3.4. Changes in drug dose and/or schedule must be discussed with and approved by the MDACC PI, or their representative prior to initiation, and will be documented in the patient record.

4.3.5. Eltrombopag will be administered primarily on an outpatient basis; but may be administered as an inpatient. Vomited doses will not be made up on the same day. If the patient misses the dose of eltrombopag in the morning they can take the daily dose no later than 5pm on the same day. Destruction of unused study drug will be in accordance with the institution's drug destruction policy.

4.3.6. Patient compliance will be documented using the MDACC Research Medication Diary and will be assessed at each study visit.

4.3.7. Study cycles will be administered every 28 days ± 7 days or upon resolution of any clinically significant study drug related AE to grade 0-1, whichever occurs first. Subsequent cycles will begin on the first day of Decitabine or Azacitidine therapy, and in the absence of toxicity, Eltrombopag administration will not be interrupted. If a subsequent cycle is delayed due to adverse events related to HMA-agent in Arm B, or if it is considered in the best interest of the patient to delay administration of HMA (e.g. because of concern for an infection), administration of the eltrombopag may continue as planned.

4.3.8. Administration of subsequent cycles may be administered when neutrophils recover to $\geq 1 \times 10^9/L$ and platelets to $\geq 30 \times 10^9/L$ or to baseline levels prior to the start of the last cycle of therapy. Patients with residual disease may start the next cycle with neutrophil and/or platelet counts lower than these if judged to be in the best interest of the patient to start the next cycle. The decision to treat should be documented in the patient's medical record.

4.3.9. Variations from the described doses and sequence may be considered on an individual basis after discussion with the PI and sponsor on a case-by-case basis.

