4.7 Dosing Delays/Dose Modifications

4.7.1 Dose adjustments for eltrombopag

The dose of eltrombopag will be adjusted according to the guidelines shown in the following tables for study drug-related clinically significant toxicity. If toxicity is not covered in the table, doses may be reduced or held at the discretion of the investigator for the patient's safety. See section 4.7.1.1. for additional liver chemistry stopping and follow-up criteria.

Patients will be withdrawn from the study if they fail to recover to CTCAE grade 0 to 1 (or within 1 grade of starting values for pre-existing laboratory abnormalities) from a clinically significant non-hematologic treatment-related toxicity within 6 weeks (leading to treatment delay of > 4 weeks) unless the investigator feels that the patient should remain in the study because of evidence that the patient is/may continue deriving benefit from continuing study treatment. Such instances will be discussed with the principal investigator on a case by case basis and the discussion documented in the medical record.

Patients with study-drug related toxicities that are manageable with supportive therapy may not require dose reductions. For patients with other drug-related toxicities, the following dose adjustment rules apply:

NCI CTCAE Grade	Action
Grade 0-2 non-hematological toxicity	No dose reduction. For grade 2 toxicities that are persistent and/or intolerable (e.g. stomatitis) patients may have a treatment interruption or dose reductions to the next lower dose level.
Grade 3-4 clinically significant non-hematological toxicity†	Hold until recover to NCI CTC AE grade 0-1 If recovery occurs within 2 weeks after treatment has been held, dose should be reduced to -1 dose level, if applicable.

† see 4.7.1.1. for additional liver chemistry stopping and follow-up criteria

Dose modifications for eltrombopag:

Dose level	eltrombopag (mg/day)
+1	300
0	200
-1	100
-2	50

4.7.1.1. Additional Liver Chemistry Stopping and Follow-Up Criteria:

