If ALT $\geq 3x$ ULN and/or bilirubin $\geq 2x$ ULN, systematic evaluation for possible causes of hepatotoxicity must be initiated, with discontinuation of any potentially offending concomitant medications (in particular statins, antifungal agents, herbal supplements) and consideration of hepatobiliary imaging as appropriate. Subjects should return to clinic for repeat liver chemistries within 24-72 hours, and then at least weekly until liver chemistries (ALT, AST, alkaline phosphatase, bilirubin) resolve or stabilize.

Treatment should be held for any of the following liver chemistry criteria (all of which confer Grade III non-hematologic toxicity per NCI CTCAE):

1. ALT \geq 5x ULN and bilirubin \geq 2.7x ULN (>35% direct bilirubin)
2. ALT \geq 8x ULN
3. ALT \geq 5x ULN but < 8x ULN and persists for \geq 2 weeks
4. ALT \geq 5x ULN if associated with the appearance or worsening of symptoms of hepatitis such as nausea, vomiting, right upper quadrant pain or tenderness.
5. ALT \geq 5x ULN but < 8x ULN and cannot be monitored weekly for \geq 2 weeks.

When any of the above criteria is met, do the following:

- Immediately withdraw investigational product
- Report the event to Novartis Oncology within 24 hours of learning of its occurrence
- Complete the SAE data collection tool if the event also meets the criteria for an SAE. All events of ALT \geq 5x ULN and bilirubin \geq 2.7x ULN (>35% direct bilirubin), modified Hy's Law for oncology clinical trials²⁶, must be reported as an SAE.

NOTE: if serum bilirubin fractionation is not immediately available, study drug should be discontinued if ALT \geq 5x ULN and bilirubin \geq 2.7x ULN. Serum bilirubin fractionation should be performed if testing is available. If testing is unavailable, record the presence of detectable urinary bilirubin on dipstick, indicating bilirubin elevation and suggesting liver injury.

- Hold eltrombopag until recovery to NCI CTC AE grade 0-1 and restart at next lower dose level regardless of recovery time.

In addition, for #1:

- Make every reasonable attempt to have subjects return to clinic within 24 hours for repeat liver chemistries, liver event follow-up assessments (see below) and close monitoring.
- A specialist or hepatology consultation is recommended.
- Monitor subjects twice weekly until liver chemistries (ALT, AST, alkaline phosphatase, bilirubin) resolve, stabilize or return to within baseline values.

For #2, 3, 4, 5:

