4.7.2. Dosing for azacitidine and decitabine-related toxicities

Patients with drug-related toxicities that are manageable with supportive therapy may not require dose reductions. For patients with other drug-related toxicities, the following dose adjustment rules apply:

NCI CTCAE Grade	Action
Grade 0-2 non-hematological toxicity	No dose reduction. Grade 2 toxicities that are persistent and intolerable (e.g. stomatitis) can result in dose delays or dose reductions to the next lower dose level in Cycle 2 or beyond.

Grade 3-4 clinically significant non-hematological toxicity	Hold until recover to NCI CTCAE grade 0-1 If recovery occurs within 2 weeks after treatment has been held, dose should be reduced to –1 dose level, if applicable.
---	---

Standard dose reductions for azacitidine and decitabine are described in the following table (please note patients should start at the dose level they were receiving prior to study enrollment):

Dose level	Decitabine (in mg/m ² for 5 days)	Azacitidine (in mg/m ² for 7 days)
0	20	75
-1	15	50
-2	10	25
-3	10 for 4 days	25 for 5 days

Patients with delayed recovery of neutrophils to $1 \times 10^9/L$ and/or platelets to $75 \times 10^9/L$ in the absence of residual disease may have dose reductions by 1 dose level in subsequent cycles.

Patients with serious infectious complications in prior cycles may have the subsequent cycles administered at one dose level reduction in subsequent cycles.

Dose reductions or delays different than those described above are acceptable after discussion with the sponsor and the PI, and will require documentation of the rationale for such action.

4.7.3. For patients with adverse events that are due to one of the two agents, dose adjustments to only one of the study drugs may be adjusted as per the guidelines mentioned above.

4.7.4. For patients on Arm B, discontinuation of the hypomethylating agent and continued therapy with eltrombopag monotherapy after cycle 2 may be considered at the discretion of the investigator.

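### Section 4.3.7 starts the next cycle at the earlier of the calendar date and adverse-event recovery, which contradicts the hold rules in 4.7; a minor safety wording error

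*Combined protocol and SAP*

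**What the plan says.** Section 4.3.7 gives two triggers for a new cycle: the calendar (28 days, plus or minus 7) or "upon resolution of any clinically significant study drug related AE to grade 0-1, whichever occurs first". The same section ties the start of a cycle to the first day of decitabine or azacitidine and then provides for the opposite case: "If a subsequent cycle is delayed due to adverse events related to HMA-agent in Arm B", eltrombopag may go on.

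The toxicity rules sit elsewhere:

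- **4.7.1, eltrombopag, grade 3-4 clinically significant non-hematological toxicity:** "Hold until recover to NCI CTC AE grade 0-1".
- **4.7.1.1, liver criteria:** "Hold eltrombopag until recovery to NCI CTC AE grade 0-1 and restart at next lower dose level regardless of recovery time".
- **4.7.2, hypomethylating agent (HMA), grade 3-4 clinically significant non-hematological toxicity:** "Hold until recover to NCI CTCAE grade 0-1".
- **4.1.2, Arm B:** for the HMA the reader is told to "see Section 4.7.2 for rules of dose reduction or delay".

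Three further clauses bear on timing. Section 4.3.8 sets neutrophil and platelet conditions for the next cycle and allows exceptions for residual disease. Section 4.3.4 says "Changes in drug dose and/or schedule must be discussed with and approved by the MDACC PI" or a representative. Section 4.3.9 allows individual variations after discussion with the PI and the sponsor.

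**The concern.** The last words of the 4.3.7 sentence select the earlier of two events. If an adverse event is still open when the calendar window closes, the calendar wins and the next cycle is due. A rule meant to make dosing wait for recovery then does the reverse.

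This is an operative dosing instruction. In Arm B a new cycle means a new HMA course, and 4.3.1 and 4.3.3 let local physicians give it, with visits to the study center required only every 3 months. Someone outside the study team may therefore be working from this sentence. On its literal terms, waiting past day 35 is itself a schedule change needing approval under 4.3.4, which places the burden on the safer course.

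**Working it through.** The plan states no figure on this point, so the check is day arithmetic followed by a comparison of texts. Days are counted from Day 1 of the current cycle.

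**Inputs**
- Calendar window C (4.3.7): 28 - 7 = day 21 to 28 + 7 = day 35.
- R: the day on which the event reaches grade 0-1. The documents give no distribution for R, so the values below are chosen illustrations.
- Hold rules (4.7.1, 4.7.1.1, 4.7.2): the held drug restarts no earlier than R. None of them has a day-35 limit.

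**Rules**
- Literal 4.3.7: due day = min(C, R).
- Hold rules combined with the schedule: due day = max(C, R) for the held drug.

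| Illustration | R | Literal 4.3.7 | Later-of rule |
|---|---|---|---|
| HMA hold starts on day 28 and resolves after the 2 weeks named in 4.7.2 | 28 + 14 = 42 | day 35 at the latest | day 42 |
| Long recovery | 50 | day 35 at the latest | day 50 |
| Early recovery | 10 | day 10 | day 21 to 35 |

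In the first row the literal date comes 42 - 35 = 7 days before the hold ends; in the second, 50 - 35 = 15 days. In the third, the literal rule brings the cycle forward to 21 - 10 = 11 days before the window opens.

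**Comparison of texts**
1. For any R beyond day 35, literal 4.3.7 and the holds give different instructions for the same drug and patient. No text says which prevails.
2. Later in 4.3.7 a cycle delayed for HMA-related events is treated as normal, and 4.1.2 refers to rules for delay. Both presuppose waiting, so the intent can be read from the document.
3. Section 4.3.8 concerns neutrophils and platelets only and does not settle non-hematological events.
4. Sections 4.3.4 and 4.3.9 govern departures from the default. They do not say what the default is.
5. The direct conflict is limited to grade 3-4 clinically significant non-hematological toxicity and the liver criteria. For grade 2, 4.7.1 and 4.7.2 make interruption or delay optional.

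**The case against.** The strongest reply is that the specific governs the general. Both drugs have an explicit hold, and no text says that a new cycle lifts it. Together with the delay language in 4.3.7 and 4.1.2 and the PI's control of schedule, a clinician would wait for recovery. This stands as to weight and applies equally to both arms. It does not remove the contradiction, because the precedence has to be inferred.

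It is also unclear whether a study-drug-related event in this sentence includes HMA toxicity. Section 4.7.1.1 uses the term for eltrombopag, while 4.7.3 counts both agents as study drugs. On the narrow meaning the conflict with 4.7.2 weakens; those with 4.7.1 and 4.7.1.1 remain.

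Three stronger readings are tempting, and the documents do not support them:

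- **That Arm B patients are exposed to HMA re-dosing during toxicity in a way that Arm A is not.** The hold in 4.7.2 protects Arm B as the hold in 4.7.1 protects Arm A.
- **That the conflict can be sized by setting the 7-day calendar tolerance against the phrase "leading to treatment delay of > 4 weeks".** That phrase belongs to the eltrombopag section and describes when a patient is withdrawn unless benefiting. It is not an allowance for delaying an HMA cycle, so the difference measures nothing relevant here.
- **That cycles would in practice be brought forward after early recovery.** The sentence literally allows it, but 4.1, 6.1 and 8.1 fix the cycle at 28 days. The case shows only that the connective is wrong.

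Finally, merely exchanging the connective and leaving the trigger as any clinically significant event would do harm. It would make grade 2 delays compulsory, override the count-based starts in 4.3.8, and let an eltrombopag-only event delay the HMA despite 4.7.3. This objection stands and shapes the fix.

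**Conclusion.** The sentence is wrong as written. Read literally, it makes the next cycle due by day 35 with a clinically significant drug-related event unresolved, contrary to the holds in 4.7.1, 4.7.1.1 and 4.7.2 and to the delay language in 4.3.7.

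It is a minor point of safety wording. The holds make the intent clear and harm unlikely in either arm. The number of patients affected cannot be estimated: the documents give no onset times, recovery times or expected rate of hold-triggering events. The toxicity rates in 8.3 are a prior mean, a stopping threshold and scenarios, not forecasts. Sample size, Simon boundaries, the toxicity stopping rule, endpoints and analyses are unaffected.

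The conclusion rests on the plain meaning of the connective and on the absence of any text giving 4.7 precedence over 4.3.7. It does not depend on the chosen values of R.

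**What to change.** Reword the sentence in 4.3.7 along these lines: *every 28 days ± 7 days or, if a drug is being held under 4.7.1, 4.7.1.1 or 4.7.2, upon recovery to grade 0-1, whichever occurs later, for the drug being held.*

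Add four short statements so that the change creates no new mandatory delay:

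- Delays for grade 2 toxicity stay optional, as in 4.7.1 and 4.7.2.
- Cycle starts that depend on neutrophil or platelet counts stay governed by 4.3.8.
- An event due to one agent need delay only that agent, as in 4.7.3; eltrombopag may still continue when only the HMA is delayed.
- The exceptions under 4.3.4 and 4.3.9 remain.

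The cost is a short wording amendment to one section, with no change to the design or the analysis.
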